#### 6.2.2 FORMULATION, APPEARANCE, PACKAGING, AND LABELING

The LL-BMT1 lenses, manufactured by Leo Lens Technology Co., Inc., are supplied freely floating in individual vials of basic saline solution [REDACTED]. The peel-off cap and rubber stopper will be removed from the vial prior to use. The extended-wear contact lenses have had bimatoprost coated onto the anterior surface of the lens.

---

#### 6.2.3 PRODUCT STORAGE AND STABILITY

The study lenses must be stored in a secure, locked location accessible only to authorized study personnel and maintained at a temperature of 2°-8°C (35.6°-46.4°F), with excursion permitted to 25°C (77°F). The lenses should also be kept away from light when stored.

---

#### 6.2.4 PREPARATION

Not applicable.

---

#### 6.3 MEASURES TO MINIMIZE BIAS: RANDOMIZATION AND BLINDING

Not applicable.

---

#### 6.4 STUDY INTERVENTION COMPLIANCE

Not applicable.

---

#### 6.5 CONCOMITANT THERAPY

Aside from study medication, antihistamines and all topical ocular medications are prohibited during the study. In addition, marijuana and any other recreational drugs are prohibited. Systemic treatments that the patient has been receiving for at least 30 days prior to study initiation are

acceptable. The medical monitor should be informed of any new systemic medications that cannot be delayed until the end of the study to determine if the patient can participate and/or continue in the study. Prior to study treatment initiation, any current glaucoma medications must be washed out using the below schedule (but washout should not commence until after written informed consent has been obtained):

- 4 days washout for parasympathomimetic and topical or systemic carbonic anhydrase inhibitors
- 2 weeks washout for sympathomimetics and alpha agonists
- 4 weeks washout for beta adrenergic blocking agents, combination product, ROCK inhibitors, and prostaglandin agonists

---

#### 6.5.1 RESCUE MEDICINE

The Sponsor will not supply rescue medication. Should the IOP at any time during the study be elevated 10 mmHg above baseline (after washout, if applicable), the lens will be removed and a different IOP-lowering medication should be prescribed at the discretion of the investigator. The patient will be discontinued from study intervention but will continue in the study.

The date and time of rescue medication administration as well as the name and dosage regimen of the rescue medication must be recorded in the electronic Case Report Form (eCRF).

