In all of these circumstances, patients should continue to attend all remaining study visits and undergo all scheduled testing.

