## 9.3 POPULATIONS FOR ANALYSES

The following populations will be analyzed:

- Safety population: Includes all patients whose eyes are in contact with LL-BMT1 lenses.
- Intent-to-treat (ITT) population: Includes all patients who have LL-BMT1 lenses successfully inserted.
- Modified intent-to-treat (mITT) population: Includes all patients who have LL-BMT1 lenses successfully inserted and complete at least 1 on-therapy follow-up assessment; only the study eye from each patient will be included in this analysis.

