6.3 Missing Data and Imputation

No Imputation will be conducted for this study.

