6.8 Secondary Analysis

There will be both safety and efficacy assessments in the secondary analysis.

The secondary safety analysis will consist of identifying the following:

- Percent of patients with ≥ 5 mmHg increase from baseline in IOP at each visit
- “Abnormal” and “Severe” slit-lamp biomicroscopy findings at the Baseline, Day 1, and Day 7 Visits
- Contact lens protein deposits at the Day 7 Visit
- Change from Baseline in CLDEQ-8 results at the Day 7 Visit

The secondary efficacy analysis will consist of identifying the change from baseline in IOP at each visit. Study eyes only within the modified intent-to-treat population will be used for this part of the analysis.

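### IOP measured after rescue with another drug enters the per-visit LL-BMT1 summary, because neither document has a rule that separates it

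*Protocol*

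**What the plan says.** Protocol 6.5.1 sets the rescue rule: "Should the IOP at any time during the study be elevated 10 mmHg above baseline (after washout, if applicable), the lens will be removed". The investigator then chooses some other pressure-lowering treatment. The patient's status afterwards is given next: "The patient will be discontinued from study intervention but will continue in the study". Footnote q to the Schedule of Activities (Protocol 1.3) repeats the rule. For patients taken off study intervention, Protocol 7.1 adds that "patients should continue to attend all remaining study visits and undergo all scheduled testing", so IOP goes on being measured. The rescue itself is documented in the eCRF: "The date and time of rescue medication administration as well as the name and dosage regimen of the rescue medication must be recorded".

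The efficacy endpoint (Protocol 9.4.3, SAP 5.2 and 6.8) is the change in IOP from baseline, visit by visit. SAP 6.8 fixes the analysis set: "Study eyes only within the modified intent-to-treat population will be used for this part of the analysis". That population is defined only in Protocol 9.3. It asks for successful lens insertion and that the patient "complete at least 1 on-therapy follow-up assessment; only the study eye from each patient will be included in this analysis". On incomplete data, SAP 6.3 says "No Imputation will be conducted for this study". SAP 1.1 records no change from the protocol.

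A secondary safety endpoint is the percentage of patients at each visit whose IOP has risen by at least 5 mmHg (Protocol synopsis and 9.4.2, SAP 5.2 and 6.8; Protocol section 3 has 10 mmHg instead). A rescue trigger reading meets either threshold.

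Neither document says how IOP taken after rescue is to be analysed.

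**The concern.** A patient who reaches the trigger has, on the protocol's own terms, failed on the lens. From then on the eye is treated with something else, yet its readings remain eligible for the table that describes what LL-BMT1 does to IOP. The trial has one arm, so there is no comparator against which to judge the mixture. It plans five treated patients, so a single such eye has real weight.

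Two summaries are exposed. The IOP mean at visits after rescue would include another drug's effect. The per-visit safety percentage could also fall back at the next visit because the other drug worked, so that a patient whose pressure rose enough to need rescue no longer counts. The IOP summary is the only efficacy output of the trial. In an open-label study, a choice made after seeing one patient's values would be post hoc.

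**Working it through.** **Does the plan's logic lead to inclusion?** Read together, the provisions do.

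1. After rescue the patient stays in the study (Protocol 6.5.1) and keeps all scheduled testing (Protocol 7.1). IOP on the other drug is therefore collected.
2. The mITT definition governs which patients enter, not which readings count. One assessment on therapy is enough, and the 4 pm reading on Day 1 or the trigger reading itself could supply it. Rescue is not an exclusion.
3. The summary is made at each visit for those study eyes (SAP 6.8), and no sentence removes or flags readings after rescue. SAP 6.3 deals with values that are absent; these are present.

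A programmer following the SAP would include the readings.

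**Which visits are affected?** Scheduled IOP after insertion falls on Day 1 (4 pm), Day 4, Day 7, Day 8 and, conditionally, Day 9. A trigger by Day 4 can affect the on-treatment readings that follow it, on Day 4, Day 7 or both. Day 8 and Day 9 are off-lens for everyone by design. Protocol 8.2 allows unscheduled visits, while the SAP 3.3 analysis windows after insertion are exactly Days 1, 4, 7, 8 and 9. A rise found on, say, Day 5 falls in no window. The +10 would then appear in no visit summary, although the later readings on the other drug would.

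**How large is it?** The documents give no expected effect, SD or rescue frequency, so there is no planned efficacy figure to reproduce. The sample size does reproduce: 5/(1 - 0.20) = 6.25, rounded up to 7, matches the stated maximum of 7 consented for 5 evaluable. I take n = 5 study eyes, each with weight 1/5 = 20%.

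Let four eyes change by c, and let the fifth reach +10, be rescued, and then read r. At a later visit:

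- as written: (4c + r)/5
- rescued eye left out: c
- trigger value kept: (4c + 10)/5

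With c = -6 mmHg (assumed) and r from -4 to -8 (assumed):

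| r | As written | Left out | Trigger value kept |
|---|---|---|---|
| -4 | (-24 - 4)/5 = -5.6 | -6.0 | (-24 + 10)/5 = -2.8 |
| -6 | (-24 - 6)/5 = -6.0 | -6.0 | -2.8 |
| -8 | (-24 - 8)/5 = -6.4 | -6.0 | -2.8 |

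As written minus left out is (r - c)/5: +0.4 at r = -4, 0 at r = -6, and -0.4 at r = -8. The sign depends on whether the rescued eye falls more or less than the others.

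Trigger value kept minus as written is (10 - r)/5, whatever c is: 14/5 = 2.8 to 18/5 = 3.6 over this range, and 10/5 = 2.0 if r = 0. Trigger value kept minus left out is (10 - c)/5 = 16/5 = 3.2.

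**Safety percentage.** One patient in five gives 20% at the visit of the trigger reading. If the other drug brings the reading below the threshold by the next visit, that patient contributes nothing there, and the percentage is 0% if no one else has risen.

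**Tests.** Protocol 9.4.1 allows an exploratory Wilcoxon test. The smallest two-sided exact p-value is 2/32 = 0.0625 with five eyes and 2/16 = 0.125 with four. No test decision at 5% turns on this point.

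**The case against.** Inclusion is inferred from silence; the plan does not expressly say that readings after rescue are kept. That is right, and it should be stated that way. But the inference is the literal reading of the stated rule, and no provision points the other way.

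A reader might infer that the plan always biases the result in favour of LL-BMT1 when it fails, by about 3 mmHg. The documents do not support that. The gap of 2.8 to 3.6 mmHg arises only against a mean that keeps the +10 reading, which is a form of carrying a value forward that SAP 6.3 does not provide for. Against simple exclusion the gap in the example is at most 0.4 mmHg, in either direction. A reader might also infer that a failure would be reported as a response. No responder endpoint exists; only the mean change is affected.

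The failure would not vanish altogether. A trigger reading at a scheduled visit stays in that visit's summary, including the maximum, and in that visit's safety percentage. Line listings (Protocol 9.4.7), medication listings (SAP 6.5) and disposition listings (SAP 6.1) would let a careful reader find one rescued patient among five. This limits the harm but does not repair the summaries at later visits, and the visit summaries miss a trigger found between windows.

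Finally, the endpoint is secondary and descriptive, the primary AE rate does not use these readings, and nothing changes unless someone is rescued. All of that stands and keeps the point modest.

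**Conclusion.** The point holds in a limited form. As written, study-eye IOP taken after rescue enters the per-visit LL-BMT1 summary, and the rescued patient can drop out of later counts of IOP increase. If one of five patients is rescued, one fifth of the later-visit mean describes another drug. In the example, neither the as-written mean (-5.6 to -6.4 mmHg) nor the mean without that eye (-6.0) shows that a patient failed; keeping the trigger value gives -2.8. Exclusion alone is therefore not enough, and the number rescued has to stand beside the mean.

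The sizes rest on assumed changes of -6 and of -4 to -8 mmHg, and on one rescue among five; the documents supply none of these. The primary endpoint is untouched. It is worth fixing because the plan's stated rule credits LL-BMT1 with another drug's effect, and the data needed to avoid this are already collected.

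**What to change.** Add to SAP 6.8, before database lock:

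- **Main IOP summary:** exclude study-eye IOP taken after another IOP-lowering drug starts, using the rescue date and time in the eCRF. List the excluded values separately. Keep the planned off-lens Day 8 and Day 9 values of patients who were not rescued; a rule worded as on-lens values only would wrongly drop them.
- **Number rescued:** show the number rescued by each visit beside the mean, including those whose trigger reading came at an unscheduled visit.
- **Safety percentage:** count a rescued patient as having had the IOP increase at all later visits.
- **Sensitivity means:** give one with all observed values and one in which the rescued eye keeps its trigger value. State the second as an exception to SAP 6.3.

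The cost is a few sentences and a little programming, with no new data and no change to any clinical rule. The downside is fewer values at later visits: four eyes instead of five in the example.

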## 7 STUDY INTERVENTION DISCONTINUATION AND PATIENT DISCONTINUATION

### 7.1 DISCONTINUATION OF STUDY INTERVENTION

Patients may be discontinued from study intervention for any of the following reasons:

- Investigator decision: The investigator can decide that the patient should be discontinued from study intervention for any reason.
- Patient decision: Patients who decide to discontinue study intervention should be explicitly asked about the contribution of possible AEs to their decision, and any AE information elicited should be documented. Preferably the patient should withdraw consent in writing and, if the patient refuses or is physically unavailable, the site should document and sign the reason for the patient's failure to withdraw consent in writing. The patient is lost to follow-up after a reasonable number of attempts to contact the patient (including documented phone calls and/or emails, and a certified letter) have been completed.
- Sponsor decision: The Sponsor or its designee can stop the patient's participation in the study for medical, safety, regulatory, or other reasons consistent with applicable laws, regulations, and GCP guidelines.
- Pregnancy: If a patient becomes pregnant during the study, the patient will be immediately discontinued from study intervention. Only pregnancies considered by the

investigator as related to study drug (e.g., resulting from an interaction between study drug and a contraceptive drug) are considered AEs unto themselves. However, all pregnancies with an estimated conception date that occurred during the study must be recorded in the AE section of the eCRF and investigators must actively follow up, document, and report on the outcome of all pregnancies.

- AE: If the investigator decides that the study intervention should be discontinued because of an AE, the investigational product is to be discontinued and appropriate measures are to be taken. The Sponsor or its designee is to be alerted immediately.
- Damage to both LL-BMT1 lenses: The investigator should take care with lens handling, especially during removal of the lens for IOP assessment. If a lens is damaged during removal, a new lens cannot be inserted in the patient's eye. Patients can remain on the study if at least one LL-BMT1 lens is able to be reinserted in one of the patient's eyes. If both lenses are damaged during removal, then the patient will not be allowed to continue with study procedures.

In all of these circumstances, patients should continue to attend all remaining study visits and undergo all scheduled testing.

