**Day 1 (Visit 6): Lens insertion**

- Concomitant medications
- AEs
- Heart rate and blood pressure - *procedure should be performed before study intervention*
- BCVA - *procedure should be performed before study intervention*
- Biomicroscopy - *procedure should be performed before study intervention*

- IOP (measured at 8 am  $\pm$ 1 hour) - *procedure should be performed before study intervention*
- LL-BMT1 insertion of new lens
- Contact lens assessment
- LL-BMT1 removal (directly before 4 pm IOP assessment) - *If a lens is damaged during removal, a new lens cannot be inserted in the patient's eye. Patients can remain on the study if at least one LL-BMT1 lens is able to be reinserted.*
- IOP (measured at 4 pm  $\pm$ 1 hour)
- LL-BMT1 reinsertion (directly after 4 pm IOP assessment)

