#### **Day 4 (Visit 7): On-treatment assessment**

- Concomitant medications
- AEs
- Heart rate and blood pressure
- BCVA
- Biomicroscopy
- LL-BMT1 removal (directly before 8 am IOP assessment) - *If a lens is damaged during removal, a new lens cannot be inserted in the patient's eye. Patients can remain on the study if at least one LL-BMT1 lens is able to be reinserted.*
- IOP (measured at 8 am  $\pm$ 1 hour)
- LL-BMT1 reinsertion (directly after 8 am IOP assessment)

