### 1.3 SCHEDULE OF ACTIVITIES

Procedures	Screening Visit 1 Day -45 to -14	Acclimation Visit 2 Day -14	Acclimation Visit 3 Day -7	Acclimation Visit 4 Day -6	Baseline Visit 5 Day 0	Lens Insertion Visit 6 Day 1	On- Treatment Visit 7 Day 4	End of Treatment Visit 8 Day 7	Follow-Up Visit 9 Day 8	Conditional Follow-Up/ End of Study Visit 10 Day 9	Early Termination Visit
Informed consent	X										
Inclusion/exclusion criteria	X				X						
Ultrasound pachymetry	X										
Humphrey visual field assessment a	X										
Demographics	X										
Medical history	X										
Insertion of nonmedicated lenses b,c	X	X		X							
Removal of nonmedicated lenses b			X		X						
Heart rate and blood pressure	X				X	X d	X	X	X	X	X
Urine pregnancy test e	X				X						
BCVA	X	X	X	X	X	X d	X	X	X		X
Biomicroscopy	X	X	X	X	X	X d	X	X			X
IOP f,q	X				X g	X d,h	X i	X j	X i	X i	X
CLDEQ-8					X k			X			X
Insertion of new LL-BMT1 lens b,c						X l					
Removal/reinsertion of LL-BMT1 lens c						X m	X m	X n			X
CL assessment o						X		X			
Concomitant medications	X	X	X	X	X	X	X	X	X	X	X
AEs	X	X	X p	X	X p	X	X	X	X	X	X

Abbreviations: AEs, adverse event; BCVA, best-corrected visual acuity; CL, contact lens; CLDEQ-8, Contact Lens Dry Eye Questionnaire-8; IOP, intraocular pressure.

aIf Humphrey visual field assessment has been completed within 6 months of Screening Visit, it does not have to be repeated at the Screening Visit.

bAll lens insertions and removals will be conducted by the investigator.

cAt the discretion of the investigator, topical anesthesia can be applied to patient's eyes prior to lens insertion.

dThese procedures should be performed before study intervention.

eUrine pregnancy test will be performed on women of childbearing potential.

fIOP will be assessed 3 minutes after lens removal, with the goal of reinserting the lens within 2-3 minutes after IOP assessment. Three measurements will be taken at each visit and these results will be averaged.

gIOP will be performed at 9 am  $\pm$ 1 hour and 4 pm  $\pm$ 1 hour.

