## 7.2 PATIENT DISCONTINUATION FROM THE STUDY

Patients will be discontinued from the study in the cases of patient death or lost to follow-up.

Patients may decide to discontinue participation in the study; any such patient withdrawing from the study will be asked to complete the Early Termination Visit assessments. The reason for patient discontinuation from the study will be recorded on the eCRF. No patients who discontinue from the study will be replaced under any circumstances.

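### Protocol 7.1 gives opposite instructions on follow-up when both LL-BMT1 lenses are damaged on Day 1 or Day 4

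*Protocol*

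**What the plan says.** Section 7.1 of the protocol lists reasons for taking a patient off study intervention. The last is damage to both lenses at removal, and for that patient the bullet ends: "then the patient will not be allowed to continue with study procedures". The next sentence closes the section for every listed reason: "In all of these circumstances, patients should continue to attend all remaining study visits and undergo all scheduled testing".

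The surrounding text points both ways:

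- **Towards stopping.** The Day 1 schema in 1.2 states "Patients can remain on the study if at least one LL-BMT1 lens is able to be reinserted". The same condition appears for Day 4 in 1.2, in footnote m of 1.3, in 6.2.1 and in the 7.1 bullet itself.
- **Towards continuing.** Section 7.2 names death, loss to follow-up and the patient's own decision as routes out of the study. Lens damage is not among them. Section 6.5.1 takes a rescued patient off the intervention but keeps that patient in the study.
- **Early Termination Visit.** Section 7.2 mentions it only for patients who choose to leave: "any such patient withdrawing from the study will be asked to complete the Early Termination Visit assessments". The 1.3 column for that visit includes heart rate/blood pressure, BCVA, biomicroscopy and IOP.

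Timing matters too. On Day 1, heart rate/blood pressure, BCVA and biomicroscopy each carry the note "procedure should be performed before study intervention". Removal for reinsertion comes just ahead of the IOP reading on both days: "LL-BMT1 removal (directly before 4 pm IOP assessment" on Day 1 and "LL-BMT1 removal (directly before 8 am IOP assessment" on Day 4. Footnote f of 1.3 adds "IOP will be assessed 3 minutes after lens removal".

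**The concern.** Two adjacent sentences in one section give opposite orders for the same event, and the SAP does not choose between them. Up to two sites could act differently, each with text to cite.

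The protocol foresaw the event: it wrote a rule for it and warns about lens handling in 6.2.1 and 7.1. A lens damaged at removal may not be replaced, patients who leave are not replaced, and the SAP imputes nothing (6.3). This is a five-patient safety study, so scheduled post-exposure examinations are its main objective safety data. Those are the data that the bar could remove.

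**Working it through.** The plan gives no figure on this point to reproduce. Its one sample-size figure, up to 7 consented, follows from 5/(1 − 0.20) = 6.25, rounded up to 7, and plays no part here. The contradiction is textual; the arithmetic only sizes it.

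**Inputs.** Five treated patients (9.2). Visit content from 1.2 and 1.3. Lenses are removed and reinserted on Days 1 and 4, so there are 2 × 5 = 10 planned occasions. Day 7 removal is final, so the reinsertion rule does not arise there.

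**Scheduled assessments after insertion, and losses per case if the bar is applied with no Early Termination Visit.** Day 9 is left out because it is conditional. The Day 4 column assumes that day's tests are done in the listed order, before removal.

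| Assessment | Per patient | Total (× 5) | Day 1 case loses | Day 4 case loses |
|---|---|---|---|---|
| BCVA | Days 4, 7, 8 = 3 | 15 | 3 of 15 | 2 of 15 |
| Biomicroscopy | Days 4, 7 = 2 | 10 | 2 of 10 | 1 of 10 |
| Heart rate/BP | Days 4, 7, 8 = 3 | 15 | 3 of 15 | 2 of 15 |
| IOP | Day 1 4 pm, Days 4, 7, 8 = 4 | 20 | up to 4 of 20 | up to 3 of 20 |

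- Damage precedes the IOP reading due at that visit. If the site still takes that reading, the IOP losses are 3 of 20 and 2 of 20.
- If all five patients had a Day 9 visit, a Day 1 case would lose 4 of 20 heart rate/blood pressure and up to 5 of 25 IOP assessments.
- In either case the biomicroscopy loss includes 1 of 5 (20%) at Day 7, the only post-exposure visit named in that endpoint (Day 1 biomicroscopy is done before insertion).
- If an Early Termination Visit is done, it supplies one of each test. The net Day 1 loss becomes 3 − 1 = 2 BCVA, 2 − 1 = 1 biomicroscopy and 3 − 1 = 2 heart rate/blood pressure.
- CLDEQ-8 is not counted as a loss. Its two-week recall would cover less than one day of LL-BMT1 wear for a Day 1 case.

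**Study-eye IOP summary.** SAP 6.8 uses the mITT population, and Protocol 9.3 requires at least one on-therapy follow-up assessment for it. For a Day 1 case the only candidate is the 4 pm reading taken just after removal.

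- Not taken, or not counted as on-therapy: the patient is outside mITT and the summary has 4 patients under either instruction.
- Counted: later visits have 4 patients under the bar and 5 under the closing sentence. In the latter case, 1 of 5 values (20%) at Days 4 and 7 is off drug.

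**The case against.** The strongest reply is that the documents largely settle the matter. The bullet sits in a list about stopping intervention, the closing sentence covers the whole list, 7.2 does not make lens damage a study exit, and 6.5.1 handles rescue in the same way. That is good evidence of what was probably intended, but it does not remove the sentence that says otherwise.

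Nor does it help to read *procedures* as lens wear only. The schedule in 1.3 uses that word to head its assessments, and the one-lens rule speaks of staying on the study, not on treatment.

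A second reply is that the Early Termination Visit would recover the tests. Nothing forbids it for these patients, and its column contains the right examinations, so the table above is a worst case. But the text asks for that visit only from patients who decide to withdraw, so it cannot be relied on here.

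A third reply is rarity: both lenses must be lost during removals done by the investigator. The documents give no probability, and none is claimed. Section 8.2 also allows unscheduled visits if a safety concern arises. Both points limit the consequence and support a minor rating.

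**Conclusion.** Section 7.1 is wrong as written, and the point is minor. The worst case for one Day 1 event is 3 of 15 BCVA, 2 of 10 biomicroscopy and 3 of 15 heart rate/blood pressure assessments, before any Day 9 visit. It assumes that the site follows the bar and does no Early Termination Visit.

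A reader might infer more than the documents support:

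- **That the safety checks are bound to be lost.** They are lost only under that combination of choices, and the better-supported reading of the protocol keeps them.
- **That the IOP summary is 4 under one instruction and 5 under the other.** This depends on whether the patient has an on-therapy assessment and so enters mITT.
- **That the primary result is at risk.** Exposure has already occurred, so the safety population and the AE-rate denominator do not change, and AE/SAE reporting continues under 8.3.
- **That the contradiction creates the SAP's lack of a rule for off-drug values.** Such values can also follow damage to the study-eye lens alone, rescue, or stopping for an AE. That gap is a separate matter.

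**What to change.** In Protocol 7.1, replace the last sentence of the lens-damage bullet with: *If both lenses are damaged during removal, study intervention stops; the IOP reading due at that visit is still taken, and the patient attends all remaining visits and undergoes all scheduled testing except the Day 7 contact lens assessment.*

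Change *remain on the study* to *remain on study intervention* in 7.1, 1.2 (Days 1 and 4), 1.3 footnote m and 6.2.1.

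No change to 6.5 is needed. Allowing IOP-lowering treatment to resume would be a new treatment policy, and it could itself produce the fall of at least 3 mmHg that triggers the Day 9 visit.

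The cost is one protocol amendment, with no change to sample size or the primary endpoint. It brings a few off-treatment values. A washed-out patient also has 8 − 1 = 7 more days of follow-up after Day 1 damage (9 − 1 = 8 with Day 9), or 8 − 4 = 4 after Day 4 damage (9 − 4 = 5 with Day 9). Rescue under 6.5.1 remains available throughout.
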